Method: The inclusion criteria of this study as follows: (a) age must be greater than or equal to 20 years old, (b) admitted to the ICU and have been intubated for at least 24 hours, (c) awareness of people, time, and place without hearing impairment., (d) be able to communicate in writing., (e) the Glasgow Coma Scale(GCS) score must be equal to or greater than 11(with a vocal response of 1 in the patient post-endotracheal tube placement). The exclusion criteria of this study as follows: (a) history of insomnia, Alzheimer's disease, or depression, (b) routine use of sedative-hypnotic drugs (opioids, benzodiazepines, non-benzodiazepines, antihistamines, and melatonin) before admission, (c) post-operation in the operating room before ICU admission, (d) intensive care delirium screening checklist(ICDSC) score of at least 4 or Confusion Assessment Method for the Intensive Care Unit (CAM-ICU) positive. *Sample:* The sample size for this study is calculated using G*Power 3.1, with an effect size set at 0.25 (Kotrlik & Williams, 2003), $\alpha = 0.05$, and power = 0.8. The minimum required sample size is 58 participants. In statistical analysis, a sample size of 30 is often considered the threshold for a large sample, the total sample size will be 60 participants, with 30 participants in the experimental group and 30 participants in the control group.

Study interventions

This study adopts a convenience sampling method and will be conducted

in the Fifth Department of Internal Medicine ICU at Kaohsiung Chang Gung Memorial Hospital. The study groups are set as follows: the white noise group will receive white noise intervention, while the conventional treatment group will receive standard care. The total sample size of 60 participants will be divided into 6 blocks of 10 participants each, with random assignment generated by a computer. Upon admission to the ICU, patients who meet the inclusion and exclusion criteria will be selected. The principal investigator will fully explain the study's purpose and procedures to the patients, and once informed consent is obtained, the recruitment process will begin. On the first day of enrollment, participants will complete a baseline assessment using the VAS sleep quality scale (T0). Random assignment will then allocate participants to either the Treat (white noise) group or the Control (standard care) group based on the generated block sequence.

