For the white noise group, in addition to receiving standard care, white noise will be introduced from 11 p.m. to 6 a.m. the following morning. A noise-reducing sleep aid device will be placed at the corner of the bedside cabinet, and a decibel meter will be positioned near the patient's head. The volume of the noise-reducing sleep aid device will be controlled between 40-50 decibels. According to a study by Van et al. in 2009, up to 90% of delirium occurs on the third day of ICU admission, so the intervention will be applied

continuously for three nights. The control group will receive standard care. Both groups will complete the VAS sleep quality scale at 6 a.m. on the first day after intervention (T1), the third day (T2), and the fifth day (T3). The total number of assessments will be four, each taking approximately 5 minutes.

Outcome measurements: The Verran and Snyder-Halpern Sleep Scale (VSHSS) was initially developed by Snyder-Halpern & Verran in 1989 to measure the sleep quality of hospitalized patients from the previous night. The internal consistency reliability was found to be 0.82. The original scale consisted of four subscales: sleep fragmentation, sleep disturbance, effective sleep, and compensatory sleep. In 1996, Simpson et al. revised the scale to include three subscales: sleep disturbance, effective sleep, and compensatory sleep. Tranner et al. tested the scale in 2003 with 110 hospitalized and surgical patients, and the Cronbach's α values for the subscales of sleep disturbance, effective sleep, and compensatory sleep were 0.86, 0.80, and 0.63, respectively. In 2007, Fang and Wang translated this scale, and the Cronbach's α values for sleep disturbance, effective sleep, and compensatory sleep were 0.90, 0.72, and 0.64, respectively. The overall internal consistency was 0.84, and the Content Validity Index (CVI) was 1.0.

The scale consists of 15 items, each scored on a 0-100mm visual analog scale, where 0 represents the lowest score and 100 represents the highest. The

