sleep disturbance section contains 7 items, with a total score range from 0 to 700. A lower score indicates more severe sleep disturbance. The effective sleep section contains 4 items, with a total score range from 0 to 400. A lower score indicates less effective sleep. The compensatory sleep section contains 4 items, with a total score range from 0 to 400. A lower score indicates a greater need for compensatory sleep. Since the original author of the scale has passed away, the version of the Verran and Snyder-Halpern Sleep Scale used in this study has been translated and authorized by the publisher.

Statistical Methods: Descriptive Statistics: Personal demographic data and disease characteristics of the study participants will be analyzed. Categorical variables will be presented as frequencies and percentages, while continuous variables will be expressed as means and standard deviations.

Inferential Statistics:Independent samples t-tests or chi-square tests will be used to compare the homogeneity of sleep quality and demographic data between the white noise group and the general care group before the intervention.

Independent samples t-tests will be used to compare the differences in sleep quality pre- and post-intervention between the white noise group and the general care group.

Generalized Estimating Equations (GEE) will be used to compare the

effects of the white noise group and the general care group under the factors of group, time, and the interaction between group and time.

Ethical considerations: Ensuring Non-Disclosure of Participants' Identity and Information: A research code will be used to represent each participant's identity during the study, ensuring that the participant's name, ID number, address, medical record number, or any other personal information will not be disclosed during the research process.

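### No planned effect analysis adjusts for the pre-randomisation sleep score (T0), which gives up precision the trial could have at almost no cost

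*Combined protocol and SAP*

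**What the plan says.** Under Study interventions, on the day of enrolment "participants will complete a baseline assessment using the VAS sleep quality scale (T0"). The next sentence begins "Random assignment will then allocate participants to either the Treat (white noise) group". T0 is therefore measured before allocation, and T1, T2 and T3 use the same scale. The section adds: "The total number of assessments will be four", a count that includes T0.

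Statistical Methods, Inferential Statistics, then plans three things:

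- T-tests or chi-square tests to "compare the homogeneity of sleep quality and demographic data between the white noise group" and the control group before the intervention. This is the only place where T0 has an explicit role.
- "Independent samples t-tests will be used to compare the differences in sleep quality pre- and post-intervention between the white noise group" and the control group. This can mean a test on change scores, or separate tests before and after the intervention.
- A GEE comparing the groups "under the factors of group, time, and the interaction between group and time". The plan does not say whether T0 is one of the levels of time.

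No baseline covariate is named in any analysis.

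**The concern.** In a randomised trial, a baseline score on the outcome scale is often the strongest available predictor of the outcome, and adjusting for it removes the variance it explains. The plan collects T0 but fixes its weight in advance, at 1 or at 0 depending on the reading. A weight of 1 does badly when T0 predicts follow-up weakly, because subtraction then adds noise. A weight of 0 does badly when T0 predicts follow-up strongly.

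The documents do not give the correlation. The scale was designed "to measure the sleep quality of hospitalized patients from the previous night", so a low night-to-night correlation is quite possible, but a moderate or high one cannot be excluded. With only 60 patients from one ICU, precision is scarce. The unsettled wording also leaves the choice between change and raw scores open until the data are seen.

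**Working it through.** **Inputs.** From the documents: 30 patients per arm, T0 before allocation, the same scale at T0 to T3. Assumed, because the documents do not give them: true difference 0.5 SD, equal SDs (set to 1) at T0 and follow-up, one follow-up visit, everyone analysed, two-sided 5% test. The T0-to-follow-up correlation rho is shown as a range. The plan states no figure for the precision of these analyses, so there is none to reproduce first.

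**Step 1: what each reading does with T0.**

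- *T-test on change:* T0 has slope 1 by construction.
- *GEE with T0 as a level of time:* on a simulated complete data set of 60, the group-by-time coefficients were 1.051, 0.870 and 0.534 under independence, exchangeable and AR(1) working correlation. The between-group differences in mean change from T0 were the same three numbers. So this is also slope 1.
- *Raw t-test after the intervention, or GEE on T1 to T3 only:* slope 0.

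**Step 2: variance per patient.**

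- Change: 2(1 − rho)
- Raw: 1
- Adjusted: (1 − rho²) × 57/56. The factor 1 + 1/(60 − 4) = 57/56 is the expected cost of chance imbalance in T0, about 1.8%.

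Before that factor, adjustment leaves (1 + rho)/2 of the change-score variance and 1 − rho² of the raw variance. At rho = 0.5 the net figure is 0.75 × 57/56 = 0.763, against 1.0 for both change and raw.

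**Step 3: power.** Noncentral t with noncentrality 0.5 × √(15/variance), on 58 df (57 when adjusted). At rho = 0.5 the noncentrality is 0.5 × √15 = 1.936 unadjusted and 0.5 × √(15/0.763) = 2.216 adjusted.

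| rho | Variance: change / raw / adjusted | Power: change / raw / adjusted | Gain over change (points) | Gain over raw (points) |
|---|---|---|---|---|
| 0.1 | 1.80 / 1 / 1.008 | 30 / 48 / 47% | 18 | −0.3 |
| 0.25 | 1.50 / 1 / 0.954 | 34 / 48 / 50% | 15 | 2 |
| 0.5 | 1.00 / 1 / 0.763 | 48 / 48 / 59% | 11 | 11 |
| 0.7 | 0.60 / 1 / 0.519 | 69 / 48 / 75% | 6 | 27 |
| 0.9 | 0.20 / 1 / 0.193 | 98.9 / 48 / 99.1% | 0.2 | 51 |

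Simulated variances (6,000 trials per rho) agreed. At rho 0.5 they were 1.01 raw, 0.98 change and 0.76 adjusted.

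**Step 4: equivalent sample size.** The per-arm number needed to match 30 adjusted is 30 × (unadjusted variance / adjusted variance). At rho 0.25, 0.5 and 0.7 this is 47, 39 and 35 for change, and 31, 39 and 58 for raw.

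**Step 5: where adjustment stops paying.**

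- Against raw: (1 − rho²) × 57/56 = 1 gives rho² = 1/57, so |rho| = 0.132.
- Against change: (1 + rho)/2 × 57/56 = 1 gives rho = 112/57 − 1 = 0.965.

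The lost degree of freedom moves the critical t only from 2.0017 to 2.0025, under 0.1 power point. The imbalance factor costs about 0.7 to 0.8 points.

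**Step 6: a rough ceiling on rho.** For the translated scale, Outcome measurements gives Cronbach's alpha for sleep disturbance, effective sleep and "compensatory sleep were 0.90, 0.72, and 0.64, respectively". If alpha is read as reliability, rho should not much exceed it. At 0.72 and 0.64 the net ratios to change are 0.875 and 0.835, and the gains over change are 5.5 and 8 points. Alpha measures consistency within one night in another sample, so this is a guide and not a bound.

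**Step 7: does the proposed GEE deliver this?** On one complete data set, the visit contrasts from a GEE on T1 to T3 with T0 and T0-by-visit (0.760, 0.061, 0.488) equalled the per-visit covariate-adjusted estimates under independence and exchangeable working correlation. In 100,000 simulated complete normal data sets per rho (0.1 to 0.9), type I error was 6.1–6.3% with the uncorrected robust standard error and z, and 5.0–5.1% with the Kauermann–Carroll correction and t on 57 df. Corrected power at rho 0.25, 0.5 and 0.7 was 49%, 59% and 75%.

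**The case against.** The planned analyses are valid, and the size of the gain rests on assumptions. Against whichever unadjusted form is better at each rho, the gain at rho 0.1, 0.25, 0.5, 0.7 and 0.9 is −0.3, 2, 11, 6 and 0.2 points, so it is material only in the middle of the range. The largest gains are against a raw comparison, whereas the t-test sentence reads more naturally as change. This is fair, but rho is unknown in advance, so nobody can choose the better unadjusted form beforehand. Against change, the more natural reading, the gain is largest at low rho.

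The alpha argument is selective. An earlier validation quoted in the protocol gives 0.86, 0.80 and 0.63. At 0.80 the net ratio to change is 0.916 and the gain about 3 points. For sleep disturbance (0.86 to 0.90) it is about 1 to 0.2 points. This stands, and Step 6 should carry little weight. It does not reverse the direction.

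Slope 1 is exact only for complete data with time as a factor. With missing visits the weight on T0 differs, and a group effect averaged over T0 to T3 would treat T0 as an outcome. Neither estimates a slope for T0. The simulations of the proposed GEE also used complete data only, so its behaviour with dropout is untested here.

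Finally, the small-sample correction is a separate matter. That is correct: the unadjusted post-only GEE contrast has 5.8–6.0% type I error without it. It is needed with or without T0, and including it does no harm.

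**Conclusion.** The concern holds. No reading of the plan estimates a slope for T0, although T0 is measured before allocation on the outcome scale. The consequence is avoidable imprecision, not bias. At rho 0.5, with a true difference of 0.5 SD and 30 per arm analysed, power is 48% under either planned form and 59% with adjustment, the equivalent of about 39 patients per arm instead of 30. The amount elsewhere depends on rho, which only the data can supply. Adjustment is at least as good as both unadjusted forms for rho between about 0.13 and 0.965, and outside that range the loss is under one power point. The effect size, equal variances, full follow-up and two-sided test are assumptions, not figures from the documents. The change should be made but is not a condition for validity.

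**What to change.** Add to Inferential Statistics, before the outcome data are analysed:

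> For each subscale score (sleep disturbance, effective sleep, compensatory sleep), the treatment effect is estimated by GEE (identity link) on T1, T2 and T3, with that subscale's T0 and T0-by-visit as covariates and group, visit and group-by-visit as factors. Robust standard errors use a small-sample (Kauermann–Carroll) correction with a t reference (57 df with 60 analysed). Group contrasts are reported with 95% confidence intervals.

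A covariate-adjusted linear model per visit, or a likelihood-based mixed model with the same terms, would also do. The planned t-tests can stay as unadjusted supporting analyses, provided the plan says whether they use change or post-intervention scores. Which subscale or visit is primary is a separate question.

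The cost is wording. T0 is already collected, so no visit, procedure or extra patient is needed. The statistical price is the lost degree of freedom and the 1.8% expected variance inflation shown above.

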Currently, the treatment of sleep disorders in ICU patients still primarily involves medication, but cognitive decline, drug tolerance, and drug dependence may lead to negative effects on sleep. Therefore, many international studies have explored non-pharmacological interventions to improve ICU patients' sleep, such as reducing light and noise stimuli, minimizing nighttime disturbances, or teaching relaxation techniques. Among these, white noise intervention is one approach to reduce light and sound stimulation. The purpose of white noise is to create a consistent sound with fixed frequencies and tones, which can raise the hearing threshold during nighttime sleep, reducing the frequency of being awakened by sudden loud noises, and thereby enhancing sleep quality through masking effects (Farokhnezhad Afshar et al., 2016).

White noise interventions have often used white or pink noise in research, typically targeting newborns, students, or healthy adults. For example, a study

on white noise in a cardiac ICU found that exposure to 40-50 decibel noise between 8-9 p.m. and 11 p.m.-12 a.m. for one hour each night for three days significantly improved sleep quality compared to the control group (Farokhnezhad Afshar et al., 2016). This suggests that the effectiveness of white noise interventions in improving ICU patients' sleep quality is inconsistent, possibly due to differences in the duration and timing of the intervention. Furthermore, sleep disturbances during the night in the ICU are unpredictable, and short intervention periods may not be sufficient to protect patients from sudden noise events that occur outside the intervention hours. Many studies on white noise in adult ICUs use the Pittsburgh Sleep Quality Index to measure sleep quality, which assesses sleep over the past month. However, since critically ill patients are in the acute phase and their ICU stay is usually short, the Pittsburgh Sleep Quality Index may not accurately reflect their sleep condition during their ICU stay. Additionally, individuals may have preferences for different types of white noise, making it difficult to standardize the type of noise used in interventions. Therefore, the purpose of this study is to explore the effectiveness of white noise interventions on sleep quality in adult ICU patients. The aim is to utilize this low-cost, easy-to-implement, and accessible measure to block out ICU noise and improve the sleep quality of critically ill patients in the ICU.

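### No primary score, visit, model term or decisive test is named and multiplicity is not controlled; if any unadjusted p < 0.05 can support benefit, the false-benefit rate is about 5–7% with three tests and, at worst, about 11–20% with nine, against 2.5% for one

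*Combined protocol and SAP*

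**What the plan says.** - **Aim** (Background and objective): "the purpose of this study is to explore the effectiveness of white noise interventions on sleep quality in adult ICU patients". No score or time point is attached.
- **Scoring** (Outcome measurements): three subscales, each with its own total. The first is described as "sleep disturbance section contains 7 items, with a total score range from 0 to 700"; effective sleep and compensatory sleep each have four items and run from 0 to 400. No 15-item total is defined. One overall reliability figure is quoted for the translated scale ("The overall internal consistency was 0.84, and the Content Validity Index (CVI) was 1.0"), so a total score is also a possible reading.
- **Timing** (Study interventions): a baseline assessment (T0), then assessments "on the first day after intervention (T1), the third day (T2), and the fifth day (T3". White noise is applied "continuously for three nights. The control group will receive standard care".
- **Analysis** (Statistical Methods, Inferential Statistics): "Independent samples t-tests will be used to compare the differences in sleep quality pre- and post-intervention" in the two groups, followed by a GEE with group, time and their interaction. The t-test sentence names no subscale and no visit. The GEE sentence does not say which term matters.
- **Error rate** (Method, Sample): alpha of 0.05 appears only in the sample-size calculation, without sidedness, outcome or test. That calculation concludes "The minimum required sample size is 58 participants", and then "the total sample size will be 60 participants, with 30 participants in the experimental group and 30 participants in the control group".

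**The concern.** The conclusion the trial wants to draw, that white noise improves sleep quality, can be reached by several routes: three subscales or a total, three visits, a t-test or a GEE term. Nothing in the plan ranks these routes or adjusts for their number. The investigators could see all the results and then report whichever score, visit or term reached p < 0.05. The 5% level (2.5% in the direction of benefit) would then describe each test but not the conclusion. The risk is practical here, because the intervention covers three nights while the last assessment is on the fifth day, so results may well differ between visits.

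**Working it through.** **1. Does the sample size identify the decisive test?** The inputs are effect size 0.25, alpha 0.05, power 0.8 and a stated minimum of 58. The effect-size metric, test and correlation are not given.

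- Two-sample t-test with d = 0.25: 252 per arm.
- One-way ANOVA with f = 0.25: 128 in total.
- Repeated-measures ANOVA, between-group effect, f = 0.25, four measurements: the noncentrality is N·f²·m / [1 + (m − 1)r]. With N = 58, m = 4 and an assumed r = 0.25 this is 58 × 0.0625 × 4 / 1.75 = 8.29, giving power 0.81. So 58 is reached, but only at that correlation; at r = 0.5 the requirement is 82.
- Regression with f² = 0.25 and five predictors: also 58.

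The figure of 58 can be reached in more than one way, each with inputs the plan does not state. It does not reveal a primary test.

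**2. How many t-tests?**

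- One: a total score at one visit.
- Three: each subscale at one visit, or a total at three visits.
- Nine: each subscale at each visit, 3 × 3.

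**3. Bounds under independence, each test two-sided at 0.05.** The chance of at least one false benefit is 1 − 0.975^k:

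- k = 1: 2.5%
- k = 3: 1 − 0.975³ = 7.3%
- k = 9: 1 − 0.975⁹ = 20.4%

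In either direction, nine tests give 1 − 0.95⁹ = 37.0%.

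**4. Correlated tests.** Simulation under no effect used normal data, 30 per arm and no missing values. The assumed correlations were 0, 0.3, 0.5 and 0.7 between subscales and 0.25, 0.5 and 0.7 between visits, exchangeable.

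| Tests that could support the claim | False benefit | Either direction |
|---|---|---|
| One | 2.5% | 5% |
| Three subscales, one visit, change scores | 5–7% | 11–14% |
| Total score, three visits, change scores | 6–7% | 12–13% |
| Nine, change from T0 | 13–18% | 26–34% |
| Nine, scores compared at each visit | 11–20% | 23–36% |

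The last two rows are both needed because the t-test sentence can mean a comparison of changes or a comparison of scores at each time.

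**5. What drives the range.** With exchangeable visit correlation r and unit variance, two changes from T0 have covariance r − r − r + 1 = 1 − r and variance 2(1 − r). Their correlation is therefore 0.5 whatever r is. In the change-score rows only the subscale correlation matters; the visit correlation has no influence. It does matter when scores are compared visit by visit.

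**6. The GEE.** With complete data and categorical time referenced to T0, each group-by-time coefficient is the same estimate as the matching difference in mean change, so it largely duplicates the t-test. Under that coding the group term is only the baseline difference. The plan does not state the coding, so no separate error rate is attached to the GEE terms.

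**The case against.** **The GEE could serve as a single test.** A joint three-degree-of-freedom test of group-by-time on one score covers all visits at once. If it were named as decisive, with the t-tests as support, the 5% level would hold however many t-tests were run. A reader might infer that the error rate fails on every reading with more than one t-test. That goes too far, because it assumes that an isolated t-test can settle the question. What stands is that the plan neither names the joint test as decisive nor chooses one score for it.

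**Nine tests is a worst case.** The documents never say that each subscale is tested at each visit, and the Study interventions section speaks of one sleep quality scale. A reader might infer that this trial's false-benefit rate is close to 20%. The documents do not support that; they only fail to rule the nine-test reading out. The three-test readings still at least double the single-test rate.

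**The correlations are assumed.** They are. A reader might also take the spread of visit correlations as evidence of robustness, but for change scores it does no work (step 5).

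**The stated purpose is to explore.** That is fair, and if meant literally it removes the need for a primary test. But the object is effectiveness, the design is randomised, and alpha and power are set, so a confirmatory reading is equally natural. The plan should say which applies.

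**Conclusion.** The gap is real and should be closed before analysis. No primary score, visit, model term or decisive test is named, and there is no multiplicity control. If any unadjusted p < 0.05 can support benefit, the false-benefit rate rises from 2.5% to about 5–7% with three tests and to about 11–20% in the nine-test worst case. Within that worst case, change scores give 13–18% and visit-by-visit scores 11–20%.

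The sizes rest on two-sided testing, 30 complete patients per arm, normal data and the assumed correlations. The existence of the inflation does not depend on the particular correlations chosen: even with both correlations as high as 0.9, nine change-score tests give about 10%. It does depend on isolated results being allowed to carry the conclusion, which the plan leaves open.

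**What to change.** Before any group comparison is run:

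1. Name one primary test: a baseline-adjusted GEE group contrast on one stated score, over stated post-baseline visits, at two-sided 0.05. The investigators choose the score and the visits.
2. Use a small-sample (t) reference. In simulation this held 4.9–5.1% (2.4–2.6% for benefit), while an uncorrected robust z-test ran at about 6%.
3. Test the other subscales with Holm only if the primary is significant, or label them exploratory.
4. Report per-visit differences with confidence intervals, and the t-tests, as descriptive.
5. If no confirmatory claim is intended, say so and label every result exploratory.
6. State whether T1–T3 are counted from the start or the end of the three nights, and restate the sample-size basis for the named test.

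**Cost.** This is a change of wording that uses data already planned. Isolated subscale or visit results can no longer be claimed at unadjusted 0.05, and power depends on the visits chosen. As an illustration, assume 0.5 SD (reading 0.25 as Cohen's f), visit correlation 0.25–0.7 and 60 complete patients. A T1–T3 average contrast then has 81–92% power if the effect is full at every visit, but 47–62% if it is absent at T3. A T1–T2 contrast has 71–88% if the effect is full at both visits. A reader might infer that dropping T3 protects the result. The unclear timing does not secure that: if the days are counted from the end of the three nights, T2 may be attenuated too.

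### The GEE plan for 60 patients names no variance estimator, test, reference distribution or small-sample correction; with an uncorrected sandwich and Wald chi-square, the joint group-by-time test would reject about 7.5% at nominal 5%

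*Combined protocol and SAP*

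**What the plan says.** The repeated-measures analysis is given in one sentence under Statistical Methods, Inferential Statistics, which applies GEE to this comparison: "effects of the white noise group and the general care group under the factors of group, time, and the interaction between group and time". Nothing more is said about how the model is fitted or tested.

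The same section also plans a simpler comparison between the arms: "Independent samples t-tests will be used to compare the differences in sleep quality pre- and post-intervention".

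The Sample paragraph under Method sets 60 patients, "with 30 participants in the experimental group and 30 participants in the control group", with a significance level of 0.05, and treats 30 as enough to count as a large sample. That remark supports the sample size; it is not made about GEE. Under Study interventions, "The total number of assessments will be four" (T0 to T3). With two arms, the interaction has 3 degrees of freedom if time is a factor.

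**The concern.** GEE inference with the sandwich variance is justified for a large number of independent patients. With 30 per arm, the uncorrected sandwich is biased downwards, because residuals around fitted means are too small. The chi-square or normal reference also ignores the fact that the variance was estimated. Both errors make p-values too small, and the joint 3-df test suffers more than a single contrast.

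The joint test is where the trial would look for a difference in course between the arms across all four assessments, and no other planned analysis does that. If the sentence is carried out with an uncorrected sandwich and a Wald test, some results would be called significant that an exact test would not support. Because the setting is left open, it could also be chosen after the data are seen.

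**Working it through.** **The plan's own figures.** The plan gives no error rate for the GEE, so there is none to reproduce. Its one calculated figure is the sample size: "The minimum required sample size is 58 participants". The stated inputs (effect size 0.25, 0.05, power 0.8) do not fix that number, because the test family, number of measurements and correlation are not given. It does come out for a repeated-measures ANOVA between-groups test with four measurements if a correlation of 0.25 is assumed (power 0.808 at 58, 0.793 at 56). Nothing below depends on it.

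**Inputs from the documents.** n = 30 per arm, N = 60; four assessments, so 4 − 1 = 3 interaction df with two arms; nominal level 0.05.

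**Assumptions.** Categorical time, complete data, normal scores, equal covariance in the two arms.

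**Step 1: distribution of the uncorrected Wald statistic.** The group-by-time model is saturated, so its estimates are the arm-by-visit means. The uncorrected sandwich is the within-arm covariance with divisor 30 instead of 29. Hence W = (30/29) × T², where T² is Hotelling's statistic on 58 df and T² = (3 × 58/56) × F(3,56).

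**Step 2: joint 3-df test.** The chi-square critical value is 7.815. W exceeds it when F(3,56) > 7.815 × (29/30) × 56/174 = 2.431, which has probability **0.0746**. A check by fitting GEE to simulated data (exchangeable working correlation, robust variance, 2,138 runs) gave 7.4%, with a Monte Carlo error of about 0.6 points. Scaling the sandwich by N/(N−1) gives 7.11%.

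**Step 3: single contrast.** P(|t58| > 1.96 × √(29/30) = 1.927) = **0.0589**, so nominal 95% intervals cover about 94.1%. If time were linear, the interaction would be a difference in mean slopes with 1 df, and the same 5.9% applies.

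**Step 4: generalized score test.** The statistic is W/(1 + W/60). It exceeds 7.815 when W > 7.815/(1 − 7.815/60) = 8.985, that is F(3,56) > 2.795, with probability **0.0485**. A single contrast gives 5.11%.

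**Step 5: which results would change.** The 5% point of F(3,56) is 2.769. This corresponds to T² = 2.769 × 174/56 = 8.605 and W = 8.605 × 30/29 = 8.902, for which the chi-square p-value is 0.031. Uncorrected joint p-values between 0.031 and 0.05 would therefore not be significant in the exact test.

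**Step 6: what restores 5%.** In this design the Kauermann-Carroll statistic equals T² and the Mancl-DeRouen statistic equals (29/30) × T².

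| Variance and reference | Joint 3-df size |
|---|---|
| Uncorrected, chi-square | 7.46% |
| Uncorrected, F(3,58) | 6.26% |
| Kauermann-Carroll, chi-square | 6.76% |
| Mancl-DeRouen, chi-square | 6.10% |
| Mancl-DeRouen, F(3,58) | 5.05% |
| Kauermann-Carroll, Hotelling-scaled F(3,56) | 5.00% |

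For single contrasts with t(58), Kauermann-Carroll gives 5.00% and Mancl-DeRouen 4.63%.

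**Step 7: price of the correction.** Single-contrast intervals widen by √(30/29) × 2.0017/1.96 = 1.039 (Kauermann-Carroll) or (30/29) × 2.0017/1.96 = 1.057 (Mancl-DeRouen). At a noncentrality of 11.69, where the exact joint test has 80% power, the uncorrected test shows 84.8%.

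**Step 8: sensitivity to assumptions not in the documents.** With 24 complete patients per arm, the uncorrected sizes are 8.17% (joint) and 6.12% (single). With strongly skewed (lognormal) scores and 30 per arm, simulation gave about 6.8% to 6.9% for the joint test.

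**The case against.** The strongest reply is that the plan never says it will use an uncorrected Wald test. A correction is unspecified, not refused, and the documents name no software from which a default could be inferred. That stands, so 7.5% must be quoted as conditional. A reader might infer that the trial's false-positive rate is 7.5%. The documents do not support this: they name no estimator and no primary test, and a score test would bring the joint test to about 4.9%.

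Second, the plan never singles out the joint 3-df test. Results read from single contrasts would be less than one point off, and the planned t-tests, if they are tests of change scores, already hold 5% for such contrasts. That also stands and limits the importance of the point. It does not remove it, because the t-tests do not test group-by-time over all assessments.

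Third, a reader might infer that the choice of working correlation never matters here. With sandwich variance and complete data it does not affect these results. With model-based standard errors it can. In a simulation with complete data and an exchangeable working model, the joint test rejected 4.9% to 5.8% when the true structure was exchangeable (correlation 0.5). The T3 contrast rejected 10.4% to 11.2% when it was AR(1) with correlation 0.6. Both structures are assumptions.

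Finally, the three subscales, with no declared primary, are a larger multiplicity issue that this correction leaves untouched: three independent tests at an exact 5% give 1 − 0.95³ = 14.3%. That is true, but it is a separate matter.

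**Conclusion.** The point holds as a conditional one. The GEE sentence leaves open settings that move the true size of the joint interaction test between about 4.9% and 7.5% over plausible sandwich-based choices. The upper figure requires categorical time, the uncorrected sandwich and a Wald chi-square; a single contrast under those settings is at about 5.9%. The figures are exact for complete normal data with 30 per arm and equal covariances; incomplete or skewed data shift them somewhat.

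The effect is minor to modest and attaches to a test that the plan does not call primary. It does not show that the planned analysis is invalid or that GEE is the wrong method. It does justify a change to the plan, because a better specification is available at small cost.

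**What to change.** Keep GEE and add to Inferential Statistics:

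- Time is a four-level categorical factor.
- Variance is a bias-corrected sandwich **and** the reference is F or t. Either use Mancl-DeRouen with F(3,58) for the joint interaction and t(58) for single contrasts, or use Kauermann-Carroll with the Hotelling-scaled F(3,56) and t(58). A corrected variance with a chi-square reference is not enough (6.1% to 6.8%).

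A REML repeated-measures model with unstructured covariance and Kenward-Roger degrees of freedom is an acceptable alternative. Fix the choice before outcome data are examined.

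**Cost.** Only the analysis wording changes; recruitment, assessments and intervention do not. Single-contrast intervals become about 4% (Kauermann-Carroll) to 6% (Mancl-DeRouen) wider than uncorrected ones. Mancl-DeRouen is slightly conservative for single contrasts (4.6%). About 5 points of apparent power are given up (84.8% to 80%), but that surplus came from the inflated size of the uncorrected test.
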